# **Data Collection Procedure**

Each participant's group will be determined by random draw.

- 20 participants will receive CNC-produced insoles.
- 20 participants will receive 3D-printed insoles.

Data will be collected through:

- Face-to-face administration of surveys
- Pressure mapping via pedobarographic analysis
- Standardized clinical measurement protocols

## **Statistical Analysis**

Statistical analysis will be conducted using **IBM SPSS 22**. Descriptive statistics (mean  $\pm$  SD) will be used for demographic and clinical variables.

- Normality testing: Shapiro-Wilk test
- Within-group comparisons (pre- and post-intervention): Paired t-test
- Between-group comparisons: Independent samples t-test
- Repeated measures (time × group interaction): Repeated Measures ANOVA
- Categorical variables: Chi-square and Fisher's Exact Test

A significance level of p < 0.05 will be considered statistically significant.

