## **Study Population and Sample**

The study population consists of individuals aged between 18 and 55 who have been clinically diagnosed with flexible pes planus and referred with a physician's prescription for custom insoles to the Orthotics and Prosthetics Department at Ondokuz Mayıs University.

Sample size was calculated using the G\*Power 3.1.9.4 software. Based on the study by Ünver and Bek (2014) that investigated the effects of insole use on plantar contact area and pressure distribution, with an alpha of 0.05, an effect size of 1.53, and a power of 0.95, the required sample size was determined to be 13 individuals per group, for a total of 26 participants. To increase statistical power and account for potential dropouts, the study will include 40 participants, divided equally into two groups (20 in each).

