## **Inclusion** Criteria

Age between 18 and 55

Diagnosed with unilateral or bilateral flexible pes planus

At least +6 on the Foot Posture Index (FPI)

 $\geq$ 5° subtalar pronation angle during standing

No foot or lower limb treatment in the last 6 months

Voluntary participation with written and verbal informed consent

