## **Randomization and Groups**

Participants will be randomly assigned to one of two groups using a simple randomization method (drawing lots).

Group 1 will receive insoles produced using CNC technology.

Group 2 will receive insoles produced via 3D printing.

Each participant will be evaluated before and after 8 weeks of insole use.

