## **Data Collection Tools and Assessment Methods**

Participants will be evaluated at baseline and after 8 weeks of insole use. The following tools will be used:

Foot Posture Index (FPI): Assesses the degree of pes planus; individuals scoring +6 or higher are eligible.

Subtalar Angle Measurement: Conducted with a goniometer while standing barefoot.

VAS-FA (Visual Analog Scale – Foot and Ankle): Evaluates pain and functional limitations specifically related to the foot and ankle. The scale ranges from worst to best function and pain levels, based on participant self-reporting.

Plantar Pressure Analysis: Using a sensor-based platform for both static and dynamic measurements of plantar contact and pressure distribution.

Quebec User Evaluation of Satisfaction with Assistive Technology (QUEST 2.0): Measures user satisfaction with the orthotic device.

Orthotics and Prosthetics Users' Survey (OPUS) – Lower Extremity Functional Scale: Evaluates lower limb functionality and daily mobility performance.

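### Both arms receive insoles, so the within-arm paired t-tests should be descriptive and conclusions should rest on the planned between-group tests

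*Combined protocol and SAP*

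**What the plan says.** Study Purpose and Importance states the aim as finding out what CNC-made and 3D-printed insoles do to foot posture, plantar pressure, pain and satisfaction. It does not say in terms that one method will be compared with the other. Randomization and Groups and Data Collection Procedure give an insole to all 40 participants, 20 by each method; no arm without insoles is described. On timing: "Each participant will be evaluated before and after 8 weeks of insole use".

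Statistical Analysis lists three relevant procedures: "Within-group comparisons (pre- and post-intervention): Paired t-test"; "Between-group comparisons: Independent samples t-test"; and "Repeated measures (time × group interaction): Repeated Measures ANOVA". One rule covers them all: "A significance level of p < 0.05 will be considered statistically significant". No test is named as primary and none is called descriptive. The section does not say whether the independent t-test is applied to change or to week-8 values.

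The sample-size paragraph reports that "the required sample size was determined to be 13 individuals per group", from an effect size of 1.53, alpha 0.05 and power 0.95.

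**The concern.** Randomisation protects one contrast here, CNC against 3D printing. Yet the listed test that appears to answer the purpose as worded is the within-arm paired t-test. That test can show that a mean changed over 8 weeks. It cannot separate an insole effect from the passage of time, repeat testing or expectation. For the Foot Posture Index (FPI) and subtalar angle, both of which have entry thresholds, regression to the mean is added if the qualifying reading is also the analysed baseline; the documents do not say whether it is.

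Two misreadings are at stake. A significant within-arm change could be reported as an insole effect. And significance in one arm but not the other could be reported as a difference between the methods, although the planned time × group test addresses that question directly.

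**Working it through.** **1. The plan's own figure.** Inputs from Study Population and Sample: alpha 0.05, effect size 1.53, power 0.95. Sidedness is not stated; two-sided is assumed. For an independent t-test with n per group, the noncentrality is d√(n/2) on 2n − 2 degrees of freedom.
- n = 12: 1.53 × √6 = 3.75, power 0.947.
- n = 13: 1.53 × √6.5 = 3.90, power 0.962.

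The stated 13 per group therefore reproduces. A one-sided independent test would need 11 per group. A two-sided paired test (noncentrality d√n on n − 1 degrees of freedom) would need 8: 1.53 × √8 = 4.33, power 0.958. The published number is thus a two-sided between-group calculation.

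**2. Significance in one arm only.** Suppose both arms of 20 have the same true standardised mean change dz (mean change divided by the SD of change). Each paired test is significant with probability p, from a noncentral t with 19 degrees of freedom and noncentrality dz√20. The arms are independent, so exactly one is significant with probability 2p(1 − p). The dz values are assumptions; results use unrounded p.

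| dz, same in both arms | p per arm | exactly one significant |
|---|---|---|
| 0 | 0.050 | 9.5% |
| 0.3 | 0.247 | 37% |
| 0.5 | 0.565 | 49% |
| 0.7 | 0.844 | 26% |
| 0.8 | 0.924 | 14% |
| 1.0 | 0.989 | 2% |
| 1.53 | above 0.999 | about 0% |

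The largest possible value of 2p(1 − p) is 50%, so dz 0.5 is near the peak.

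**3. Change not due to the insole.** With the same formula, a shift from time, repeat testing or expectation of dz 0.2 makes a paired test significant 13.6% of the time, and dz 0.3 makes it 24.7%. The documents give no basis for choosing a value.

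**4. Regression to the mean in FPI.** This applies only if the qualifying reading is the baseline. All inputs except the cut at 6 are assumed. The expected fall is (1 − r) × SD × φ(a)/(1 − Φ(a)), with a = (6 − mean)/SD and r the reliability. Example with SD 3, mean 9, r = 0.7: a = −1 and φ/(1 − Φ) = 0.242/0.841 = 0.288, so the fall is 0.3 × 3 × 0.288 = 0.26 points. Simulated paired-test significance with no insole effect, n = 20 and r from 0.9 down to 0.7:
- SD 3: 5.8–7.7% at mean 9, 7.0–11.2% at mean 8, 11.8–28.0% at mean 6.
- SD 2: 5.2–5.6% at mean 9.

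This model has no true individual variation between visits. Adding mean-zero true change with an SD of 1–2 points (at SD 3) gives 5–10% at means 8–9 and 7–24% at mean 6. Subtalar angle was not quantified.

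**5. The randomised comparison.** With two visits, the time × group F statistic is the square of the independent t statistic on change. Any shift shared by both arms cancels. With 20 per arm the noncentrality is d√10 on 38 degrees of freedom:
- d = 0.5: 1.58, power 0.338.
- d = 0.8: 2.53, power 0.693.
- d = 0.91: 2.88, power 0.801.

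The 95% CI half-width is t(0.975, 38) × √(2/20) = 2.024 × 0.316 = 0.640 SD.

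**The case against.** The strongest reply is that nothing in the plan is an error. The paired t-test is a valid test of mean change, both suitable between-group tests are already listed, and the trial was sized for a between-group test. The purpose names both technologies and can be read as comparative. On this view, the point concerns a possible misreading of results not yet written. Much of this stands. A reader might infer that the plan intends to claim an insole effect from the paired tests; it nowhere says so. A reader might also see a contradiction in calling the trial controlled when both arms are treated; there is none, since an active comparator is a control.

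The magnitudes are also open to challenge. Every input other than 1.53, the FPI cut, alpha and the group size is assumed. It would be too strong to say that regression to the mean seriously distorts the paired tests. At source means of 8–9, the more plausible range for diagnosed and referred patients, the effect is small, and at SD 2 and mean 9 it is close to nominal. The one-arm-only problem fades once changes are large: at dz 1.53 it disappears, although the plan does not give 1.53 as a paired effect size.

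What survives does not depend on those inputs. The within-arm tests cannot attribute change to the insole, they share the randomised comparison's significance rule, and no sentence says which of them decides. Naming the deciding test does not choose among the outcomes; that is a separate matter.

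**Conclusion.** The point holds as a cheap improvement to an unranked analysis plan, not as a numerical error or an invalid test. The structural part rests on the text alone: the purpose is worded as insole effects, all participants receive insoles, and uncontrolled within-arm tests stand on the same 0.05 footing as the randomised comparison. The size of the one-arm-only misreading depends on the assumed common change: with 20 per arm it runs from 9.5% with no change, through 49% at dz 0.5, to 14% at 0.8 and 2% at 1.0. Regression to the mean is a conditional and probably minor contributor. Confidence is medium, because the harm arises only if within-arm results are read as insole effects or compared across arms.

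**What to change.** In Statistical Analysis:
- Report within-arm change as descriptive and uncontrolled, as mean change with 95% CI, and do not compare within-arm p-values across arms.
- For outcomes measured before and after (FPI, subtalar angle, VAS-FA, plantar pressure, OPUS), rest conclusions on the time × group test, equivalently the independent t-test on change, with the between-group difference and its 95% CI.
- For QUEST 2.0, described under Data Collection Tools and Assessment Methods with the words "Measures user satisfaction with the orthotic device", a score before the insole is worn has no clear meaning. Use the independent t-test on the week-8 score, with its 95% CI.

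In Study Purpose and Importance, either word the aim as a comparison of CNC-produced with 3D-printed insoles, or keep it and state that within-arm change is uncontrolled and will not be claimed as an insole effect. The first option narrows the objective, which is for the sponsor to decide.

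The cost is text edits, with no new data and no new test. Within-arm efficacy claims are given up. Conclusions then rest on a test with 80% power only at d of about 0.91 and 34% at d = 0.5, so an inconclusive result is likely if the two methods differ only modestly.

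### No between-group analysis adjusts for baseline, and the plan does not say which of its two between-group tests decides CNC versus 3D printing

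*Combined protocol and SAP*

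**What the plan says.** Two sections provide for a baseline and a week-8 measurement. Randomization and Groups says "Each participant will be evaluated before and after 8 weeks of insole use", and Data Collection Tools and Assessment Methods says "Participants will be evaluated at baseline and after 8 weeks of insole use".

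The Statistical Analysis section lists two between-group procedures for continuous outcomes: "Between-group comparisons: Independent samples t-test" and "Repeated measures (time × group interaction): Repeated Measures ANOVA". It then sets one threshold for everything: "A significance level of p < 0.05 will be considered statistically significant". It does not state which values enter the t-test, which procedure answers the CNC versus 3D question, or any model with baseline as a covariate.

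Study Population and Sample derives 13 per group from an effect size of 1.53, and raises this to 20 per group for power and dropouts. The effect size comes from an earlier study of insole use. The section does not describe it as a difference between CNC and 3D-printed insoles.

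**The concern.** In a two-group trial with two visits, the interaction test is the same as a t-test on change scores. It uses baseline only by subtraction, which amounts to fixing the regression slope at 1. A t-test on week-8 values fixes the slope at 0. ANCOVA estimates the slope from the data.

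Which planned test is more precise depends on r, which the documents do not give, so naming either one in advance is a bet on r. Leaving both in place without naming one keeps the choice open until the results are known. The trial was enlarged from 26 to 40 partly to gain power, and the choice of test can add to that gain or give it back.

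**Working it through.** **The plan's own figure.** A two-sided two-sample t-test (noncentral t) with alpha 0.05 and d = 1.53 gives power 0.962 at 13 per group and 0.947 at 12. The stated 13 per group at 95% power is reproduced. At 20 per group the power is 99.7%.

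**Inputs from the document.** n = 20 per group; alpha 0.05, taken as two-sided; two visits.

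**Assumptions, not in the document.** r = 0.3, 0.5, 0.7 or 0.8; true differences of 0.5 and 0.8 in units of the week-8 SD; baseline SD equal to k times the week-8 SD, with k = 1 or 0.8; one value per participant; everyone completes.

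**Variance factors (week-8 SD = 1).**
- Week-8 t-test: 1
- Change score, which is the interaction: 1 + k² − 2kr
- ANCOVA: (1 − r²) × [1 + 1/(2n − 4)] = (1 − r²) × (1 + 1/36) = (1 − r²) × 1.028. The 2.8% is the cost of estimating the slope; it is 1/22 = 4.5% at 13 per group.

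Example, k = 1 and r = 0.5: change 1 + 1 − 1 = 1.00; ANCOVA 0.75 × 1.028 = 0.771. The ratio to the better planned test is 0.771, equivalent to 20 / 0.771 = 25.9 per group.

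| | r = 0.3 | r = 0.5 | r = 0.7 | r = 0.8 |
|---|---|---|---|---|
| Change factor, k = 1 | 1.40 | 1.00 | 0.60 | 0.40 |
| ANCOVA factor | 0.935 | 0.771 | 0.524 | 0.370 |
| ANCOVA / better planned test, k = 1 | 0.935 | 0.771 | 0.874 | 0.925 |
| Equivalent n per group, k = 1 | 21.4 | 25.9 | 22.9 | 21.6 |
| ANCOVA / better planned test, k = 0.8 | 0.935 | 0.918 | 1.008 | 1.028 |
| Interaction / ANCOVA, k = 1 | 1.50 | 1.30 | 1.14 | 1.08 |
| Week-8 t-test / ANCOVA | 1.07 | 1.30 | 1.91 | 2.70 |

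Simulation with 200,000 replicates per cell agrees with the ratios to the better planned test to within 0.002.

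**Power at 20 per group, k = 1.**

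| | r = 0.3 | r = 0.5 | r = 0.7 | r = 0.8 |
|---|---|---|---|---|
| Difference 0.8: week-8 t-test | 69% | 69% | 69% | 69% |
| Difference 0.8: interaction | 55% | 69% | 89% | 97% |
| Difference 0.8: ANCOVA | 72% | 80% | 93% | 98% |
| Difference 0.5: week-8 t-test | 34% | 34% | 34% | 34% |
| Difference 0.5: interaction | 26% | 34% | 51% | 68% |
| Difference 0.5: ANCOVA | 36% | 42% | 57% | 72% |

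**The open choice.** In a numerical check the interaction F equalled the squared t on change scores (both 0.0892), so the two listed tests differ only if the t-test is on other values. If it is on week-8 values, simulation at a difference of 0.8 shows the two tests disagreeing on significance in 29% to 31% of trials with k = 1, and in 24% to 30% with k = 0.8. If, in addition, either result may count as positive, the false-positive rate per outcome is 8.4% to 9.6%. It stays at 5% if the t-test is on change scores, is only a baseline comparison, or one test is named.

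**The case against.** The other side is that this is a preference between valid methods. Both planned tests are conventional and unbiased, and the interaction already uses baseline. Every figure for the gain rests on assumed values of r, SD ratio and effect, and at some of them the gain is small: 69% against 72% power at r = 0.3 with the week-8 t-test, and 97% against 98% at r = 0.8 with the interaction. At the plan's own effect of 1.53 the choice makes almost no difference with 20 per group. The disagreement and 9% figures depend on readings the plan does not state.

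Most of this stands as a limit on the size of the point. It does not remove it.
- The near-ties occur only when the better planned test happens to be the one used. Across r = 0 to 0.8 and both SD ratios, ANCOVA's worst loss to either planned test is 2.8% of variance. The week-8 t-test can have 2.70 times ANCOVA's variance, and the interaction 1.50 times within r = 0.3 to 0.8.
- The reassurance at 1.53 is narrower than it looks. With 13 per group completing, r = 0.3 and equal SDs, the interaction has about 88% power. Both arms receive custom insoles, so a smaller difference is plausible.
- The entry thresholds for Foot Posture Index and subtalar angle could shrink the baseline SD, and that is where ANCOVA's gain could vanish. But the cells where it does (k = 0.8, r = 0.7 or 0.8) need regression slopes of 0.7/0.8 = 0.875 and 0.8/0.8 = 1.0. Selecting on baseline also lowers r while leaving the slope unchanged, so thresholds alone do not make those cells likely.

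**Conclusion.** The concern holds as an improvement to efficiency and pre-specification. It is not an error of validity: the sample-size figure reproduces and neither planned test is biased.

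With 20 complete per group, ANCOVA's variance relative to the better planned test runs from 22.9% lower (equal SDs, r = 0.5) to 2.8% higher (SD ratio 0.8, r = 0.8). In confidence-interval terms, at r = 0.5 with equal SDs, the mean 95% half-width falls from 0.64 SD under either planned test to 0.56 SD. No gain specific to this trial can be stated, because r is not in the documents. The practical weight lies in differences well below 1.53. The change should be made, with moderate confidence in how much it will yield.

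**What to change.** 1. For each outcome with a baseline value, name as the single deciding between-group analysis an ANCOVA of the week-8 value on group and that outcome's own baseline. Report the adjusted mean difference (3D-printed minus CNC) with its 95% CI.
2. For those outcomes, label the independent t-test and the time × group ANOVA as supportive, and state which values the t-test uses.
3. Keep the independent t-test as the deciding analysis for outcomes with no baseline. QUEST 2.0 is a likely case, since it "Measures user satisfaction with the orthotic device" and so may have no meaningful value before the insole is supplied.
4. For foot-level measures, state which one value per participant enters the model, because unilateral and bilateral cases are both eligible.

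The cost is a few sentences, written before week-8 data are examined. No participants, visits or measurements are added, the sample size is unchanged, and SPSS 22 fits the model. The choice of a primary outcome, multiplicity across outcomes and the handling of non-normal outcomes are separate matters that this change does not settle.

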### **Study Title**

# The Effects of Custom-Designed 3D Printed and CAD-CAM Insole on Foot Posture, Plantar Pressure Distribution, and Satisfaction in Individuals with Flexible Pes Planus

### **Study Purpose and Importance**

The purpose of this study is to investigate the effects of custom-designed insoles manufactured using Computer Numerical Control (CNC) and 3D printing technologies on plantar pressure distribution, foot posture, plantar force distribution, foot pain, and satisfaction in individuals diagnosed with flexible pes planus. This research aims to contribute to evidence-based practice in orthotic interventions.

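### No primary outcome or multiplicity rule: six independent outcomes, each tested once at p < 0.05, give about a 26% chance of a false CNC versus 3D-printing difference

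*Combined protocol and SAP*

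**What the plan says.** The relevant text is spread over four sections of the combined protocol and SAP.

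- **Study Purpose and Importance** gives the targets of the comparison as a flat list: "plantar pressure distribution, foot posture, plantar force distribution, foot pain, and satisfaction in individuals diagnosed with flexible pes planus".
- **Study Population and Sample** rests the sample size on an earlier study that "investigated the effects of insole use on plantar contact area and pressure distribution". It does not say which variable in that study gave the effect size, and it calls neither contact area nor pressure primary.
- **Data Collection Tools and Assessment Methods** lists six instruments: Foot Posture Index (FPI), subtalar angle, VAS-FA, plantar pressure analysis, QUEST 2.0 and OPUS. None is ranked above another. Plantar pressure alone yields several variables, since it is described as "Using a sensor-based platform for both static and dynamic measurements of plantar contact and pressure distribution".
- **Statistical Analysis** assigns tests by type, not by outcome. Two of them compare the groups: "Between-group comparisons: Independent samples t-test" and "Repeated measures (time × group interaction): Repeated Measures ANOVA". The section ends with "A significance level of p < 0.05 will be considered statistically significant".

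No section names a primary outcome, a decisive contrast, a hierarchy or a multiplicity adjustment.

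**The concern.** The trial is randomised to compare two ways of making insoles. Under this plan, a significant result on any instrument, by either group test, can be presented as the finding that the methods differ. The headline outcome and test can be chosen after the results are known, and a reader could not tell a planned result from a selected one. The 5% error rate holds for each test separately but not for the overall claim that CNC and 3D-printed insoles differ. A false claim of that kind would work against the stated aim of informing evidence-based orthotic practice.

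**Working it through.** **Inputs from the documents.** Per-test level 0.05 (Statistical Analysis); six instruments (Data Collection Tools and Assessment Methods); 20 per group, and a calculation "with an alpha of 0.05, an effect size of 1.53, and a power of 0.95" giving 13 per group (Study Population and Sample); two visits, baseline and 8 weeks (Randomization and Groups).

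**Inputs not in the documents, so assumed.** The correlation between outcomes; the pre-post correlation; the number of plantar pressure variables tested; whether both group tests are applied to each outcome; and whether QUEST is analysed post-treatment only (it is described as "Measures user satisfaction with the orthotic device", yet the section's lead-in schedules every tool at both visits).

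**Step 1: the plan's own figure.** For a two-sided two-sample t-test with d = 1.53, the noncentrality is d√(n/2). Power is 0.947 at n = 12 and 0.962 at n = 13. The stated 13 per group is therefore reproduced, as the sample size for a single test at 0.05.

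**Step 2: six independent outcomes, one group test each, no true differences.**

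P(at least one p < 0.05) = 1 − (1 − 0.05)^6 = 1 − 0.7351 = 0.265.

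If plantar pressure supplies three variables, there are eight outcomes: 1 − 0.95^8 = 0.337.

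**Step 3: correlated outcomes, one test each.** With a common correlation ρ and c = 1.96, the probability is

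1 − ∫ φ(z) [Φ((c − √ρ z)/√(1 − ρ)) − Φ((−c − √ρ z)/√(1 − ρ))]^k dz.

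| ρ | k = 6 | k = 8 |
|---|---|---|
| 0 | 0.265 | 0.337 |
| 0.3 | 0.241 | 0.300 |
| 0.5 | 0.207 | 0.250 |
| 0.7 | 0.164 | 0.191 |
| 0.9 | 0.108 | 0.119 |

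Simulating actual t-tests with 20 per group (160,000 runs) gives 0.265, 0.210 and 0.166 for k = 6 at ρ = 0, 0.5 and 0.7, in line with the table.

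**Step 4: either planned group test counts.** With two visits, the time × group interaction is equivalent to a t-test on change from baseline. The simulation counted a false positive if the week-8 t-test or the change t-test was significant on any of the six outcomes. QUEST was left out of the interaction, and the pre-post correlation was 0.5.

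| ρ between outcomes | Either test significant | Range over pre-post correlation 0.2 to 0.8 |
|---|---|---|
| 0 | 0.410 | 0.398 to 0.422 |
| 0.5 | 0.334 | 0.323 to 0.350 |
| 0.7 | 0.273 | 0.257 to 0.285 |

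At ρ = 0.9 a smaller simulation gives about 18% to 19%. The paired t-tests within each group are not counted anywhere, because they do not compare the two insoles.

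**Step 5: can the trial afford a rule?** On the plan's d = 1.53, 20 per group gives power 0.997 for one primary test at 0.05. Even Bonferroni over all six outcomes (0.05/6 = 0.0083) leaves power 0.976 and holds the familywise rate at 1 − (1 − 0.0083)^6 = 0.049.

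**The case against.** The strongest reply is that 26% overstates the problem. Independence gives the highest figure among non-negatively correlated outcomes, and these instruments overlap: FPI and standing subtalar angle both describe foot posture, and VAS-FA and OPUS both cover function. This is fair, and 26% should be read as the top of a range of about 11% to 26% for six single tests. Even 11% is more than twice the nominal level, however.

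The count of six can also be questioned. The purpose statement lists five domains, and five independent tests would give 1 − 0.95^5 = 23%. Against that, all six tools are scheduled at both visits, and several plantar pressure variables would push the count up.

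The two group tests might also be meant for different situations: the interaction for pre-post outcomes and the t-test for single-time comparisons. On that reading the figures in step 4 do not arise. The text does not settle the matter, so those figures show what the plan permits, not what will necessarily be done.

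Finally, the sample-size basis hints at plantar contact area or pressure as the main outcome. A hint is not a designation: no variable is named, and the analysis section gives that domain no special standing. Nor do the documents call the study exploratory; it is described as a randomised controlled trial powered at 0.95.

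**Conclusion.** The concern holds. As written, the plan lets any of at least six unranked outcomes, by either of two group tests, carry the conclusion at an unadjusted 0.05. With one test per outcome, the chance of at least one false group difference is 26% under independence, about 21% at a correlation of 0.5, 16% to 17% at 0.7 and 11% at 0.9. If either group test may count, it is about 41%, 33%, 27% and 18% to 19% at the same correlations.

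All these figures suppose no true difference on any outcome. They illustrate the size of the problem and are not the trial's actual error rate, because the documents do not give the correlations, the number of pressure variables or the allocation of tests to outcomes. The absence of a primary outcome and of a multiplicity rule depends on none of these assumptions. The plan should be changed.

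**What to change.** Add to the Statistical Analysis section, before any outcome data are examined by group:

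> The primary outcome is [one named plantar contact-area or pressure variable]. The primary analysis is [one named between-group contrast], tested at two-sided 0.05. All other outcomes and tests are secondary.

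The sponsor must fill both brackets, because the sample-size paragraph gives only the domain. The sponsor should also confirm that the effect size of 1.53 applies to the chosen variable and contrast.

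For the secondary outcomes, list one variable per instrument and state one group test for each, so that the choice between the t-test and the interaction is closed there too. Then either apply Holm's adjustment across that list, or report estimates with 95% confidence intervals and make no significance claim. Which of the two is partly a matter of preference in a trial of 40, and either would do.

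The study period runs to December 31, 2025. If group results have already been seen, the report should say when the primary outcome was chosen, since late wording is not pre-specification.

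The cost is protocol and SAP wording plus the check on the effect size. No participants, visits or measurements are added. The downside is that fewer secondary results can be called significant.
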